3.4 Clinical Evaluation

This pilot study will evaluate usability - the safety, efficacy and performance of HidraWear AX in the home setting. Quality of life, ease of use and comfort of Hidrawear AX will be assessed.

The clinical effect of the wound pad will not be assessed. HldraWear AX does not claim wound healing but is a quicker and easier way to dress wounds.

CE-GAX001-01

V4.0

CR: 144

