6.3.4 Criteria for Withdrawal or Discontinuation

Subjects may withdraw from the study at any time without any rationale and without compromising their future medical care.

The subject may also be removed from the study by their physician or the consultant if they feel it is the best interest of the subject.

The use of the Hidrawear garment will be suspended if the patient presents with pyrexia and/or infection.

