6.4.3 Follow-up Medical Care

Subjects will remain under the care of their GP throughout the study.

CE-GAX001-01

V4.0

CR: 144

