7 STATISTICAL CONSIDERATIONS

7.1 Statistical Design

This pilot study is a small-scale preliminary investigation to evaluate feasibility, time, cost, adverse events and improve upon the study design prior to performance of a full-scale investigation. The data collected will provide the estimates needed of the potential treatment effect and the likely variability in the response at baseline and over time.

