15.4 Serious Adverse Event

A Serious Adverse Event (SAE) is any event (whether or not associated with the investigational device) that:

- Results in death
- Leads to serious deterioration in the health of the subject, that either resulted in
- Life threatening illness or injury, or
- Permanent impairment of a body structure or a body function, or
- In-subject or prolonged hospitalization, or
- Medical or surgical intervention to prevent life threatening illness or injury or permanent impairment to a body structure or body function.
- Leads to foetal distress, foetal death or a congenital abnormality or birth defect

CE-GAX001-01

V4.0

CR: 144

This includes device deficiencies that might have led to a serious adverse event if a) suitable action had not been taken or b) intervention had not been made or, c) if the circumstances had been less fortunate. These are handled under the SAE reporting system.

Planned hospitalisation for a pre-existing condition, without serious deterioration in health, is not considered a serious adverse event.

Subjects who experience and adverse will be released to their primary care provider/GP and excluded from the study.

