15.6 Reporting Adverse Events

Any and all adverse events shall be captured by our independent trial implementation partner, The Clinical Research Platform Ireland.

Adverse events will be reported in accordance with MEDDEV 2.12-1 GUIDELINES ON A MEDICAL DEVICES VIGILANCE SYSTEM and QP025 Clinical Evaluation procedure.

When an event/incident occurs, a report is necessary; the event is recorded within the records outlined in QP025 Clinical Evaluation procedure, Appendix 1: Clinical Operations Document Listing by either the SMO, Research Coordinator or Investigator and returned to HidraMed Solutions within the timelines outlined in QP025 Clinical Evaluation procedure.

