16.2 Requirements for subject follow up

In the event of suspension of whole clinical investigation, subjects shall be contacted by our independent trial implementation partner, The Clinical Research Platform Ireland to inform the subject of the premature suspension of the investigation.

A day 21 nurse visit shall be conducted whether the investigation runs to completion or not.

CE-GAX001-01

V4.0

CR: 144

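### Section 15.4 excludes subjects from the study after an adverse event (type not named), and the protocol states no later safety follow-up for them

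*Combined protocol and SAP*

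**What the plan says.** The rule is the last sentence of section 15.4: "Subjects who experience and adverse will be released to their primary care provider/GP and excluded from the study". The SAE definition above it applies whether or not the event is related to the device.

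Safety is part of the study's stated purpose. Section 3.4 says: "This pilot study will evaluate usability - the safety, efficacy and performance of HidraWear AX in the home setting". Section 7.1 says: "This pilot study is a small-scale preliminary investigation to evaluate feasibility, time, cost, adverse events".

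Other provisions bear on a subject who has an event:

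- **Capture.** Section 15.6: "Any and all adverse events shall be captured by our independent trial implementation partner, The Clinical Research Platform Ireland". Record content and timelines are left to the sponsor's procedure QP025, which is not among the supplied documents.
- **Onset.** Section 4.3 has the subject stop the device and contact the research nurse. Section 4.6 adds, for pyrexia, a temperature recheck after one hour, GP referral if it persists, and a nurse judgement on device relatedness.
- **Medical care.** Section 6.4.3: "Subjects will remain under the care of their GP throughout the study".
- **Removal.** Section 6.3.4: "The subject may also be removed from the study by their physician or the consultant", where they judge this to be in the subject's interest. The same section suspends the garment for pyrexia or infection.
- **Study-level stop.** Section 16.2 opens: "In the event of suspension of whole clinical investigation, subjects shall be contacted by our independent trial implementation partner". It closes: "A day 21 nurse visit shall be conducted whether the investigation runs to completion or not".

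**The concern.** The rule ends data collection in exactly the subjects who had an event. The onset of the event is captured, but its resolution, and anything that follows, is not secured in the study data. GP care protects the subject, but the protocol states no route by which GP findings return to the study.

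The side effects listed in section 2.4 are local: dermatitis, infection, irritation and abrasion. A repeat armpit examination could show them, and the schedule has only one after baseline. Under section 6.3.6 an excluded subject can also be replaced from a waiting list, so a full cohort at the end could hide incomplete safety follow-up.

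The missing noun adds a second problem. Site staff cannot tell whether a mild skin reaction or only a serious event triggers exclusion. If any AE does, section 15.4 conflicts with sections 4.3, 4.6 and 6.3.4, which stop or suspend the device and leave the subject in the study.

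**Working it through.** The plan gives no figure on this point to reproduce. The check has two parts.

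**1. Does any other provision supply follow-up after a 15.4 exclusion?**

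| Section | What it provides | Covers an excluded subject after release to the GP? |
|---|---|---|
| 4.3, 4.6 | Nurse contact, one-hour recheck, GP referral, relatedness judgement | No: these steps concern onset |
| 6.3.4 | Case-by-case removal; garment suspension | No: no assessment listed after removal |
| 6.4.1 and Appendix 1 | AE row from Day 0 to Day 21 | Not stated either way |
| 6.4.3 | GP care | Care only: no return of data to the study |
| 15.6 | Capture of all AEs; records under QP025 | No follow-up period or outcome record stated |
| 16.2 | Contact and a Day 21 nurse visit | Tied by its section heading and first sentence to suspension of the whole investigation; no mention of the armpit assessment |

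None states a later safety contact, an outcome record or a Day 21 armpit assessment for one excluded subject.

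**2. What is lost, by day of event?**

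Inputs, all from the section 6.4.1 schedule: daily survey on Days 1 to 21; checkup calls on Days 7 and 14; armpit assessment on Days 0 and 21; device use from Day 1. For an event on Day *d*, with that day's contacts completed, the scheduled contacts remaining are:

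- surveys = 21 − *d*
- calls = 2 if *d* < 7; 1 if 7 ≤ *d* < 14; 0 if *d* ≥ 14
- armpit assessments = 1 for any *d* from 1 to 20

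| Event day | Surveys lost | Calls lost | Armpit assessments lost |
|---|---|---|---|
| 1 | 21 − 1 = 20 | 2 | 1 |
| 10 | 21 − 10 = 11 | 1 | 1 |
| 20 | 21 − 20 = 1 | 0 | 1 |

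The Day 21 armpit assessment is the only one after baseline, so it is lost for every event before Day 21. An event first found at the Day 21 visit does not lose it. No event rate or distribution of event days is assumed.

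**The case against.** The strongest counter-argument is that the gap may not exist in practice. Section 15.6 hands event records to QP025, and outcome fields would normally sit there. This stands as a limit: the gap is shown in the protocol text, not in the sponsor's procedures. It does not answer the rule itself, which ends participation.

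Second, the Day 21 sentence in section 16.2 is worded without qualification and could be read as a promise to every enrolled subject. Section 16.1 also lists unanticipated adverse events as grounds for suspension, which would trigger 16.2. But that route depends on the whole study being suspended. An anticipated event, or an unanticipated one that does not lead to suspension, gets nothing from it.

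Third, exclusion need not mean that all contact ends, and the AE row in the schedule runs to Day 21 without exemption. That is a possible reading, but nothing says that capture continues after exclusion, and a site following the sentence literally would stop.

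Fourth, section 4.6 drops the same noun where it plainly means an adverse event, so the SAE reading is less secure than the sentence's position suggests. This is fair. It makes the any-AE reading more plausible and the conflict with 4.3, 4.6 and 6.3.4 more serious.

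Finally, this is a 23-subject, three-week pilot of a garment rated mostly low risk, and section 6.1.3 lists no safety endpoint. Daily surveys on temperature and dressings would also tell little about a subject in hospital. Both points limit the practical impact, and precautionary removal is a choice the sponsor may make. Neither explains why removal should be automatic, or why it should end safety observation.

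**Conclusion.** The concern holds. Followed as written, section 15.4 removes from study follow-up the subjects who matter most for the safety question, and no supplied section puts that follow-up back. For an event between Day 1 and Day 20 the loss is 1 to 20 daily surveys, up to two calls and the only post-baseline armpit assessment.

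The conclusion assumes that exclusion from the study ends scheduled contacts and that QP025 does not override this. The number of subjects affected cannot be estimated from the documents; under the SAE reading it may be none. The ease-of-use analysis is not at issue here. This should be corrected, with medium confidence given the missing noun and the unseen procedure.

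**What to change.** Amend section 15.4 to:

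1. Name the event type (AE or SAE).
2. Replace exclusion from the study with stopping the device where required, and leave removal to the case-by-case rule in 6.3.4.
3. Unless consent is withdrawn, keep the subject in safety follow-up through Day 21. Use the existing check-ins with one added question on event status, since the present three cover only temperature, dressings used and comments. Carry out the Day 21 armpit assessment at the clinic or at home. For a subject off the device, omit the HidraWear demonstration, ratings and nurse form, and record them as not done with the reason.
4. Record the outcome of the event, with one further contact if it is unresolved at Day 21.

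The cost is a short amendment and one extra check-in question, with ethics committee approval before use (section 10). The check-ins and the Day 21 visit are already scheduled. The burden is a few contacts with subjects no longer using the garment, and one more contact for an event still open at Day 21.

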15.5 Definition: Unanticipated Serious Device Effect (USADE)

A Serious Adverse Device Event (SADE) is an adverse device effect that has resulted in any of the consequences characteristic of a serious adverse event.

15.6 Reporting Adverse Events

Any and all adverse events shall be captured by our independent trial implementation partner, The Clinical Research Platform Ireland.

Adverse events will be reported in accordance with MEDDEV 2.12-1 GUIDELINES ON A MEDICAL DEVICES VIGILANCE SYSTEM and QP025 Clinical Evaluation procedure.

When an event/incident occurs, a report is necessary; the event is recorded within the records outlined in QP025 Clinical Evaluation procedure, Appendix 1: Clinical Operations Document Listing by either the SMO, Research Coordinator or Investigator and returned to HidraMed Solutions within the timelines outlined in QP025 Clinical Evaluation procedure.

15.7 Reporting Device Deficiencies

Any device deficiencies observed during the investigations shall be documented and controlled and processed by Hidramed Solutions.

A root cause analysis shall be undertaken by Hidramed Solutions Design & Development and Quality Assurance teams, with appropriate steps taken to remove risk of future reoccurrence.

16 STUDY SUSPENSION OR PREMATURE TERMINATION

16.1 Criteria for suspension of whole clinical investigation or in one or more sites

The study may be terminated by the Sponsor or the Investigator at any time. Criteria for suspension or premature termination of the whole clinical investigation include, but is not limited to:

- Occurrence of Unanticipated Adverse Event(s)
- Occurrence of Unanticipated Device Effect(s)
- Any other clinical reasons as identified by the Sponsor or Investigator
- Business decisions of the sponsor. This is not expected.

In the case of temporary suspension documented justification for recommencing the study, signed by the PI, will be required.

16.2 Requirements for subject follow up

In the event of suspension of whole clinical investigation, subjects shall be contacted by our independent trial implementation partner, The Clinical Research Platform Ireland to inform the subject of the premature suspension of the investigation.

A day 21 nurse visit shall be conducted whether the investigation runs to completion or not.

CE-GAX001-01

V4.0

CR: 144

17 PUBLICATION POLICY

Commitment to Publish Results

The results of the clinical investigation may be submitted for publication in clinically relevant publications

A summary of the results will be provided to subjects in lay terms.

The trial will be registered on clinicaltrials.gov

CE-GAX001-01

V4.0

CR: 144

19 APPENDIX 1. STUDY SCHEMATIC

Procedures & Assessments	V1;	Day	Day	Day	Day	Day	V2;
	Baseline Day 0	1 - 6	7	8 - 13	14	15 - 20	End of Treatment
							Day 21
Informed Consent	Х						
Medical / HS History	Х						
Armpit Clinical assessment	Х						X
Inclusion/exclusion criteria	Х						
Observe Subject using usual method of dressing wound	Х						
Dermatology Quality or life index survey, Ease of Use, Comfort, Time, Pain scale.	Х		Х		Х		Х
Subject trained on use of Hidrawear AX	Х						
Subject trained on use of Thermometer	Х						
Subject daily use of Hidrawear AX		Х	Х	Х	Х	Х	Х
Temperature Record	Х	Х	Х	Х	Х	Х	X
Observe Subject using Hidrawear AX							Х
Daily Survey		Х	Х	Х	Х	Х	Х
Checkup phone call			Х		Х		
Data Entry	Х	Х	Х	Х	Х	Х	Х
Adverse Events	Х	Х	Х	Х	Х	Х	Х

CE-GAX001-01

V4.0

CR: 144

10. Have you ever had a dressing leak/move or fall off? Yes/No

11. How long do you typically spend doing dressing changes and tending to your lesions on a daily basis?

0-5	6-10	11-15	16-20	21-25	26-30	31-35	36-40	41-45	Over 45
minutes									

- 12. Do you think that your wound care needs are being met by current dressing options? Yes/no/maybe (please elaborate)
- 13. How satisfied are you with current dressings in terms of

Comfort - scale 0-10

Ease of application, adjustment and removal (a full dressing change) – scale 0-10

Confidence it won't leak, move or fall off scale 0-10

- 14. Do you believe that wound care / dressing changes are a contributing factor to a reduced quality of life for you? Yes/No/Don't Know
- 15. Does managing your wounds / dressings impact negatively on:

Work life yes/no Social life and hobbies yes/no Sex and relationships yes/no Day to day activities yes/no Mental health yes/no Financial well being yes/no

General wellbeing yes/no

16. Please tell us, in your own words about your experiences of home management/ dressings for HS. How does it make you feel?

For example- What is your biggest frustration with dressings? Does it impact your daily life? Any problems you experience when doing your dressing changes. Do you need a mirror, extra equipment, assistance? What is the worst part about it and how do you manage on a daily basis?

Section 4: HS information and Support

CE-GAX001-01

V4.0

CR: 144

1. Where do you find your information on HS?

Doctors/	Information	Online patient	Meeting other	Other (please
Healthcare Websites		forums/groups	patients	specify in
				comment)

2. What do you think would help you feel more supported in managing your HS? What would you like to see? Please elaborate in comments.

Thank you for participating in our survey. Your time and effort will directly contribute to the publication that highlights the daily impact of HS wounds and wound care on the patient's life.

If some of the questions have made you feel upset about your HS, please visit the following sites for information and support:

https://irishskin.ie/ask-our-dermatology-nurse/

https://hopeforhs.org/

CE-GAX001-01

V4.0

CR: 144

21 APPENDIX 3 – SUBJECT ASSESSMENT FORM DAY 0

Subject Assessment Day 0

[figure not shown]
Please dress your wound using your usual product and method.

While you are dressing your wound, please pay close attention to the following:

[figure not shown]
- How easy/difficult it is
- Is it time consuming for a full dressing change
- How comfortable/uncomfortable is a dressing change
- Do you experience dressing related pain
- How confident are you that your dressing will not leak or move.

Once the dressing change is complete, please answer the following:

1. Is it easy/difficult to change your dressing using your current product and method? Please indicate the level of difficulty involved.

2. How time consuming is a dressing change using your current product and method?

Page 45 of 56

[figure not shown]
The Master Copy of this document is electronically approved and maintained as an electronic record

CE-GAX001-01 V4.0

CR: 144

[figure not shown]
3. How Comfortable is it to use and wear your current dressing?

4. Do you require pain killers before a dressing change? Please tick

Yes	No

5. Do you experience dressing related pain using current product?

[figure not shown]

CE-GAX001-01

[figure not shown]
V4.0

CR: 144

6. How confident are you that your current dressing will not leak or move?

7. How confident do you feel in yourself about your body image – self confidence/self esteem?

CE-GAX001-01

V4.0

CR: 144

22 APPENDIX 4 – SUBJECT ASSESSMENT FORM DAY 21

[figure not shown]
Please dress your wound using HidraWear AX

While you are dressing your wound, please pay close attention to the following:

[figure not shown]
- How easy/difficult it is
- Is it time consuming for a full dressing change
- How comfortable/uncomfortable is a dressing change
- Do you experience dressing related pain
- How confident are you that your dressing will not leak or move.

Once the dressing change is complete, please answer the following:

8. Is it easy/difficult to change your dressing using HidraWear AX? Please indicate the level of difficulty involved.

9. How time consuming is a dressing change using HidraWear AX?

Page 48 of 56

The Master Copy of this document is electronically approved and maintained as an electronic record

[figure not shown]

CE-GAX001-01

V4.0

CR: 144

[figure not shown]
10. How Comfortable is it to use and wear HidraWear AX?

11. Do you require pain killers before a dressing change? Please tick

Yes	No		

12.
Do you experience dressing related pain using HidraWear AX?

[figure not shown]

CE-GAX001-01

[figure not shown]
V4.0

CR: 144

13. How confident are you that HidaWear AX will not leak or move?

14. How confident do you feel in yourself about your body image – self confidence/self esteem?

CE-GAX001-01

V4.0

CR: 144

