6.1.4 Methodology

Before the study commences on site, a survey will be shared into select closed patient groups online, to capture the patient experience of living with Hidradenitis Suppurativa (HS) in terms of self-managing wound care and the impact that HS wound care has on patients' day to day life, physically, financially and emotionally.

A secure and confidential survey tool (Typeform) will be used. This is governed under EU data legislation and encrypted to ensure privacy. The survey will not collect any identifying information and is a precursor to the HidraWear AX Pilot Study.

Day 0

Subjects will visit trial site or have a home visit from research nurse.

Following consent and enrolment, Subjects will be asked to demonstrate or explain their usual method of dressing their wound using their usual wound dressing products.

Subjects will assess this activity based on ease of use, comfort, experienced pain, confidence in dressing retention and time, using a 10 point visual analogue scale. (see appendix 2)

The subjects will complete a Dermatology Quality of Life Index Survey. (see appendix 5)

The research nurse will assess the activity based on whether the subject needs assistance, uses additional equipment, contorts or stretches their body, can dress the wound without raising their arms above their head. (See appendix 4)

Day 1-21

Daily Check in with Subjects:

Each day, at 1pm, subjects will receive an email requesting them to check in with the researcher by answering 3 questions.

- 1. What is your temperature?
- 2. How many dressings did you use in the last 24 hours?
- 3. Any comments?

This check in should take less than 5 minutes to complete.

Subjects will be required to respond by 5pm each evening. If subject has not responded by 5pm, a reminder text message will be sent to them.

If subject does not respond within 24 hours, the research nurse will call the subject to check in and take answers over the phone.

CE-GAX001-01

V4.0

CR: 144

Weekly Check in with Subjects:

On day 7 and 14 subjects will be asked to complete the Dermatology Quality of life survey and questions on Ease of use, comfort, pain and confidence, at home. A link to the surveys will be emailed to them at 1pm in the afternoon with their daily check in.

Subjects will be required to respond by 5pm each evening. If subject has not responded by 5pm, a reminder text message will be sent to them.

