If subject does not respond within 24 hours, the research nurse will call the subject to check in and take answers over the phone.

Day 21

Subjects will return to site or be visited by research nurse for review.

Subjects will be asked to demonstrate how they dress their wound using HidraWear AX.

Subjects will assess this activity based on ease of use, comfort, experienced pain, confidence in dressing retention and time, using a 10 point visual analogue scale. (see appendix 3)

The subjects will complete a Dermatology Quality of Life Index Survey. (see appendix 5)

The research nurse will assess the activity based on whether the subject needs assistance, uses additional equipment, contorts or stretches their body, can dress the wound without raising their arms above their head. (See appendix 4)

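### The ease, time and pain items fix no reference period and Day 0 lets a subject only explain her method, so Day 0 and Day 21 scores may not rate the same thing

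*Combined protocol and SAP*

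**What the plan says.** For both visits Section 6.1.4 states: "Subjects will assess this activity based on ease of use, comfort, experienced pain, confidence in dressing retention and time". The activity differs by day. On Day 0, "Subjects will be asked to demonstrate or explain their usual method of dressing their wound using their usual wound dressing products"; Section 4.4 gives the same two options. On Day 21, "Subjects will be asked to demonstrate how they dress their wound using HidraWear AX", with no option to explain instead.

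The forms are in Appendices 3 and 4. The Day 0 form opens with "Please dress your wound using your usual product and method", and the Day 21 form gives the matching instruction for HidraWear AX. Both then ask the subject to attend to ease, time, comfort, pain and confidence during the change, and continue: "Once the dressing change is complete, please answer the following". The items themselves are general. Time on Day 0 is "How time consuming is a dressing change using your current product and method". Pain is "Do you experience dressing related pain using current product" on Day 0 and "Do you experience dressing related pain using HidraWear AX" on Day 21. The ease item, which supplies the primary endpoint in Section 6.1.3, has the same form: whether it is easy or difficult to change the dressing with the named product.

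**The concern.** The primary endpoint is a within-subject difference in one rating between Day 0 and Day 21, in a single-arm, unblinded study. Such a difference is interpretable only if the two ratings have the same object. If Day 0 captures what a woman generally thinks of a product she may have used for years, and Day 21 captures one change she has just done, part of the difference comes from the change of object rather than the change of product. There is no control group in which that part would show up and could be subtracted. Ease, time and pain are all exposed to this.

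**Working it through.** No figure in the plan depends on this point, so the main check is a comparison of texts.

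**Step 1: what is to be rated.** Section 6.1.4 ties the rating to the activity at the visit on both days. The form lead-ins agree: dress, attend, then answer.

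**Step 2: what the items ask.** The visible ease, time and pain items refer to a dressing change in general or to using the product. None mentions the change just completed. Other instruments in the protocol are more specific: the nurse forms (Appendix 5) ask in the past tense what the subject did, and every DLQI item (Appendix 6) fixes a one-week period.

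**Step 3: whether a change has taken place.**
- Day 21: yes, under both Section 6.1.4 and the form.
- Day 0: yes under the form, and the schedule in Section 6.4.1 lists observation of the usual method. Under Sections 4.4 and 6.1.4, not necessarily.

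A subject who only explained her method has not met the form's opening instruction and has no completed change at the visit to rate. She can answer only from earlier experience. This is the clearest route to a mismatch, and it exists on Day 0 alone.

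**Step 4: whether parallel wording cancels the effect.** The experience that a general answer draws on is unequal. Participation lasts 3 weeks, so HidraWear experience at Day 21 is at most that. Prior use of the subject's own product has no limit.

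Let *f* be the share of subjects whose Day 0 rating comes from general experience, and *b* the mean gap between that rating and the one they would give to a change just done. Let *g* and *c* be the same quantities on Day 21. Then

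shift in mean change (Day 21 minus Day 0) = *g·c* − *f·b*.

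Identical wording removes the shift only if *g·c* = *f·b*, which nothing in the plan ensures.

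**Step 5: size.** The documents give none of *f*, *b*, *g* or *c*. For illustration only, set *g·c* = 0, so that the absolute shift is *f* × |*b*| on the 10-point scale:

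| assumed *f* | \|*b*\| = 0.5 | \|*b*\| = 1 | \|*b*\| = 2 |
|---|---|---|---|
| 0.25 | 0.125 | 0.25 | 0.5 |
| 0.5 | 0.25 | 0.5 | 1.0 |
| 1 | 0.5 | 1.0 | 2.0 |

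The sign follows that of *b*, which is also unknown. So wide a range shows only that the documents do not settle the size.

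**Step 6: the plan's own precision figure.** Section 7.2 gives a margin of error of 0.18 at n = 23, without an SD or confidence level. Read as a 95% t half-width for a mean, it implies SD = 0.18 × √23 / 2.074 = 0.42. Read as a 95% half-width for a proportion of 0.5, n = 23 gives 1.96 × √(0.25/23) = 0.204 instead. The figure can be neither confirmed nor refuted, and it cannot serve as a yardstick for the shift.

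**The case against.** The strongest defence is the lead-in. Both forms tell the subject to dress the wound, to notice the aspects later scored, and to answer straight afterwards. The attention list uses the same present tense for the change in progress, so tense alone does not turn an item into a question about habit. This stands for a subject who performed a change on Day 0: the wording leaves a residual ambiguity under a sound instruction. It does not help a subject who only explained her method.

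The rating scales are figures that are not reproduced, so anchor text may exist. The absence of a reference period can be stated only for the visible text.

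General experience is also a defensible target. Section 5.1 compares against existing product use, and Section 3.1 speaks of the patient's experience. But Section 6.1.4 chose the activity at the visit, and either target must be the same on both days.

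Two stronger readings are tempting. The first is that the bias favours HidraWear, because Section 6.1.3 cites user frustration and Section 2 says current dressings often leak or move. The documents do not establish that direction. Long practice with one's own product could raise general Day 0 ease ratings, and early learning with a new garment could lower general Day 21 ratings.

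The second is that the shift could by itself produce a statistically significant improvement. With an assumed share of 0.75 and gap of 2 points, the shift is 0.75 × 2 = 1.5. With an assumed SD of change of 2.5, the 95% half-width at n = 23 is 2.074 × 2.5/√23 = 1.08. But share, gap and SD are all assumptions. After the anticipated loss of up to 6 subjects (n = 17) the half-width is 2.120 × 2.5/√17 = 1.29. Sections 7.1 to 7.3 describe a pilot giving estimates, with no test or significance level against which to call a result significant.

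**Conclusion.** The point holds as a mismatch in what is measured. Section 6.1.4 and the lead-ins aim at the change at the visit, the items do not say so, and the Day 0 option to explain contradicts the Day 0 form. Some Day 0 scores, including the primary ease score, may reflect general experience while Day 21 scores reflect a change just performed. Size and direction are unknown, and the plan does not provide for recording how many Day 0 subjects only explained their method. The conclusion rests on the visible text of the forms and on Section 6.1.4 being applied as written. It does not invalidate the endpoint, but the forms should be corrected because the repair is cheap and the design has no control group.

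**What to change.** 1. Reword the ease, time and pain items identically on both forms, apart from the product name, so that they refer to *the dressing change you have just done*.
2. On Days 7 and 14 the ratings are completed at home by emailed link, with no observed change described. Use *your most recent dressing change* for whichever of these items are asked. Section 6.1.4 and the schedule list slightly different sets. The Week 2 versus Week 1 ease endpoint should benefit as well.
3. Reconcile the Day 0 text in Sections 4.4 and 6.1.4 with the Day 0 form and the schedule. The rewording alone fails for a subject who only explained her method, because it gives her nothing to rate. If explaining stays permitted, state what she is to rate.
4. Record on the Day 0 nurse form whether a change was actually performed.
5. Repeat the primary comparison in subjects who performed a change on both days, and report how many did. This is a descriptive sensitivity check in a subset that may be selected.
6. Leave the comfort item general, since it covers wearing the dressing as well as changing it.

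The cost is form wording, one tick box and one extra analysis, with no added visits. The downside is that a score for a single change does not capture the usual variation between changes.
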